2.3.1.1 Summary of Phase-I Safety Information

In Part 1, treatment-emergent adverse events (TEAEs) were reported in 16.7% of ABBV-4083-treated subjects and 0% of placebo-treated subjects. The most common (≥ 5%) TEAEs for ABBV-4083-treated subjects were nausea (8.3%) and headache (5.6%). A single subject in the 100-mg group experienced Grade-1 elevated alanine aminotransferase (ALT) on Study Day 3, resolving on Study Day 14.

In Part 2, TEAEs were reported in 58.3% of ABBV-4083-treated subjects (66.7% in fasting subjects and 50.0% in fed subjects). The most common (\geq 10%) TEAEs for ABBV-4083-treated subjects were nausea (25.0%), diarrhoea (16.7%), headache (16.7%), hepatic enzyme increased (16.7%) and vomiting (16.7%). During the fasting period, 2 subjects experienced asymptomatic and reversible elevated ALT and/or aspartate aminotransferase (AST) values at Grade 1. In the fed period, 2 subjects experienced mild adverse events (AEs) of elevated serum liver enzymes leading to discontinuation of study drug: one subject experienced asymptomatic and reversible Grade-2 elevated ALT and/or AST 6 days after receiving a single 1000 mg dose of ABBV-4083, and 1 subject experienced asymptomatic and reversible Grade-4 elevated ALT and/or AST 3 days after receiving a single 1000 mg dose of ABBV-4083. No accompanying total, direct, or indirect bilirubin elevations were observed. The Investigator considered the AEs to have a reasonable possibility of being related to ABBV-4083. The effect of food on exposure parameters, i.e. C_{max} or area under the blood concentration-time curve (AUC), was minimal.

Independent internal and external drug-induced liver injury experts were consulted. In accordance with their advice, the single dose of 400 mg was tested again in Part 1 Group 6 (n = 6 subjects) with extended monitoring from 3 to 10 days. No above normal transaminase levels were observed. This was followed by the MAD portions of the study (Part 3) with the same extended monitoring period.

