- · an IMP-related treatment-emergent AE leading to discontinuation, i.e. considered as having a reasonable possibility of being related to any of the IMPs, and with onset between Day 0 and 30 days after the end of treatment;
- a severe or serious IMP-related treatment emergent AE, i.e. considered as having a reasonable possibility of being related to any of the IMPs, and with onset between Day 0 and 30 days after the end of treatment;
- a Grade 3 or 4 ALT elevation during treatment, defined as between Day 0 and 2 days after the end of treatment; ALT elevations will not additionally be counted as AEs described in the previous two criteria, although they may be reported as AEs.

The SRC and DSMB will continue to monitor the toxicity criteria in Part 2, and the safety results will be cumulative from Part 1 to Part 2. That is, subjects with an event meeting the toxicity criteria during Part 1 will still count in Part 2 for the same treatment, as if the study was not paused between Part 1 and Part 2. If > 10% of subjects in any regimen meet the toxicity criteria across Parts 1 and 2, the regimen will halt but dose adjustment will not occur in Part 2. Safety will be reviewed by the SRC and DSMB using the same criteria for any arms in Part 1 that are restarted using the 300 mg ABBV-4083 dose.

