3.5.2.3 Dose-adjusted Arms in the Event of Toxicity

If > 10% of subjects in an arm of Part 1 meet any of the toxicity criteria, the actions shown in Table 1 may be implemented. Decisions for dose reduction will be taken based on all available safety data including the events that trigger the dose adjustment process.

Table 1. Dose Adjustment Recommendations for Toxicity Management in Part 1		
Toxicity criteria	Recommended action	Rationale
reached in		

Toxicity criteria	Recommended action	Rationale
reached in		
Arm A or Week 1 of Arm B	Halt all study arms, then begin to enrol new Arm F, Arm G, Arm H and/or Arm I with a reduced dose of ABBV-4083 300 mg QD (n=30/arm), continue to enrol the remainder of Arm E in Arm J (to a total n=30).	Presumes that dose of ABBV-4083 is too high and that albendazole does not add to the observed toxicity.
Week 2 of Arm B	Halt Arm B, then begin to enrol new Arm G with ABBV-4083 300 mg QD (n=30)	Presumes that dosing ABBV-4083 400 mg QD is safe for 7 days but not 14 days.
Arm C	Halt Arm C, then begin to enrol new Arm H with ABBV-4083 300 mg QD (n=30)	Presumes that dosing ABBV-4083 + albendazole 400/400 mg QD is safe for 3 days but not 7 days.
Arm D	Halt Arms C and D, then begin to enrol new Arms H and I with ABBV-4083 300 mg (n=30/arm)	Presumes that dosing ABBV-4083 + albendazole 400/400 mg QD is not safe.

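### The toxicity rule stops counting Grade 3-4 ALT 2 days after treatment, so a late rise in the 14-day regimen, or a Day 13 value in a Part 2 7-day regimen, may not count

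*Protocol*

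**What the plan says.** Protocol 3.5.2.2 lists three ways for a subject to count as a toxicity. Two are IMP-related treatment-emergent adverse events: those leading to discontinuation, and those that are severe or serious. Both run to 30 days after the end of treatment. The third is "a Grade 3 or 4 ALT elevation during treatment, defined as between Day 0 and 2 days after the end of treatment". It is followed by: "ALT elevations will not additionally be counted as AEs described in the previous two criteria, although they may be reported as AEs". More than 10% of an arm meeting any criterion sends the matter to the DSMB in Part 1. In Part 2 the regimen halts, and the count is cumulative: "subjects with an event meeting the toxicity criteria during Part 1 will still count in Part 2 for the same treatment".

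Protocol 2.3.1.1 reports two liver-enzyme events after single 1000 mg doses: "asymptomatic and reversible Grade-4 elevated ALT and/or AST 3 days after receiving a single 1000 mg dose of ABBV-4083" and "asymptomatic and reversible Grade-2 elevated ALT and/or AST 6 days after receiving a single 1000 mg dose of ABBV-4083". After expert advice, 400 mg was retested "with extended monitoring from 3 to 10 days". "This was followed by the MAD portions of the study (Part 3) with the same extended monitoring period".

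Table 1 (3.5.2.3) has a row for toxicity in Week 2 of Arm B, with the rationale: "Presumes that dosing ABBV-4083 400 mg QD is safe for 7 days but not 14 days".

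**The concern.** Altered liver tests are the one potential safety effect that Protocol 2.3.2 says is under consideration, yet ALT has the shortest window of the three criteria. The Phase I programme lengthened liver follow-up because rises came late. The present rule does not carry that over, and the available text gives no reason.

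The effect is uneven across arms. The 7-day Part 1 arms take placebo in the second week, which keeps their window open well past the last active dose. Arm B has the longest exposure and gets no such margin. A Grade 1-2 ALT seen at the Day 13 visit that reaches Grade 3 on Day 17 during adverse-event follow-up would, read literally, count nowhere. Part 2 could also count a value differently from Part 1 for the same regimen, in a total that pools the two.

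**Working it through.** The protocol states no operating characteristics for this rule, so there is no figure of the plan's own to reproduce.

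**Windows.** Dosing runs from Day 0 to Day 13 in every Part 1 arm (Appendix 1, footnote 17). Take end of treatment as the last capsule.
- Adverse-event criteria: 13 + 30 = Day 43.
- ALT criterion: 13 + 2 = Day 15.
- Arm B, last active dose Day 13: the window closes 15 − 13 = 2 days later. A 3-day delay gives 13 + 3 = Day 16, which is outside.
- Arms A, C and D, last ABBV-4083 dose Day 6: the window closes 15 − 6 = 9 days later. A 3-day delay gives Day 9, which is inside.
- If end of treatment meant end of exposure (one day after the last dose, 3.5.2.2), the cutoff is Day 16 and an exact 3-day delay just counts.
- Part 2, 7-day regimen without a placebo week: 6 + 2 = Day 8, so a Day 13 ALT is outside. Whether there will be a placebo week is open (Appendix 2, footnote 17).

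**Last scheduled liver test.** Tables 7 and 8 schedule laboratory safety tests at Day 13 and then at Month 3. Tables 9 and 10 place the Day 13 serum pregnancy test on the biochemistry tube. That test is taken at least 24 hours after the last dose (9.3.3.9.3). The last sample is therefore at about Day 14. Later results can come only from unscheduled testing (9.1; Appendix 1, footnote 20) or adverse-event follow-up (9.3.4.10).

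**Size.** The available text gives no Grade 3-4 ALT rate at 400 mg, so the rates below are assumptions. Model: a dose on day d produces a rise visible from day d + 3, and the Day 14 sample sees it if d + 3 ≤ 14, that is d ≤ 11.
- Any of 14 doses equally likely to be the trigger: Days 0-11 are seen, a share of 12/14.
- Only second-week doses (Days 7-13): Days 7-11 are seen, a share of 5/7.

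Crossing 10% of 30 subjects needs 4. Single look at n = 30, P(X ≥ 4) with X ~ Binomial(30, rate × share):

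| True rate | All rises counted | Any dose (12/14) | Second week only (5/7) |
|---|---|---|---|
| 10% | 35% | 25% | 16% |
| 15% | 68% | 55% | 40% |
| 20% | 88% | 78% | 64% |

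Simulation of repeated looks: 30 subjects accrued uniformly over an assumed 12 months, looks every 0.46 month once 15 are treated, events known 0.5 month after entry, flag when the count exceeds 10% of those treated. At a 15% rate, the chance of a flag is about 85% (all counted), 77% (any dose) and 67% (second week only). Using only subjects followed for 0.5 month as the denominator adds about 2 points to each. At a 5% rate the figures are about 25%, 20% and 14%.

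These gaps measure what a Day 14 last sample misses. A wider window alone recovers only the rises that unscheduled or follow-up testing happens to find.

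**The case against.** **The clause on not counting ALT additionally has another purpose.** It could be argued that a no-double-counting clause does nothing in a rule that counts subjects, so this one must exclude late rises. That does not follow. Inside the window it also stops a Grade 1-2 ALT rise that leads to discontinuation from counting under the first criterion, and Phase I had a Grade 2 case of that kind. Exclusion of late rises is the literal reading but not the only one. This objection stands, and it is a reason to clarify the text.

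**The evidence for delay is thin.** A reader might apply the 6-day delay and infer that the rule is almost blind in Arm B. The documents do not support this: the 6-day event was Grade 2 and would meet the criterion under no window. The 10 days is a monitoring length, not an observed delay. What remains is one subject at 3 days, at 2.5 times the trial dose. Section 2.3.2 reports no hepatotoxicity at 400 mg for up to 14 days, though Phase I had only 6 subjects on that regimen (zero of 6 has a one-sided 95% upper limit of 1 − 0.05^(1/6) = 39%). Part of the Phase I safety summary is not in the reviewed copy.

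**The last sample is not before the last dose.** Because dosing-day samples are drawn pre-dose (9.3.3.9.1), a reader might place the Day 13 liver test before the final dose and infer a much larger loss. Tables 9 and 10 point to about Day 14 instead.

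**Other safeguards exist.** Potential drug-induced liver injury is a listed example of a serious event (9.3.4.3), a clinical diagnosis replaces a laboratory value where available (9.3.4.2), and dose decisions use all safety data (3.5.2.3). SAP 10.3 shift tables include the final post-baseline value. These soften the consequence but do not put a late Grade 3-4 ALT into the 10% count.

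**The Part 2 mismatch is conditional.** It needs a 7-day regimen without a placebo week. Month 6 ivermectin or placebo is also an IMP, so end of treatment in Part 2 could even be read as Month 6. That adds to the case for defining the term.

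**Conclusion.** The point holds as a moderate gap in a safety rule that is cheap to close. As worded, Grade 3-4 ALT after Day 15 in the 14-day regimen does not clearly count, while other drug-related events count to Day 43. The Part 2 count may also treat a 7-day regimen's Day 13 ALT differently from Part 1.

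At an assumed 15% rate and a 3-day lag, the chance of a flag in Arm B falls from about 85% to 77%, or to 67% if only second-week doses matter. The second restriction has little support, since concentrations on Days 1 and 14 appeared similar (2.3.1.2). If the true rate at 400 mg is near zero, nothing is lost.

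A reader might go further and conclude that ABBV-4083 is hepatotoxic at 400 mg, or that monitoring is inadequate without an added visit. The documents support neither conclusion.

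**What to change.** In Protocol 3.5.2.2:
- Define end of treatment as the last dose of ABBV-4083, albendazole or their matching placebo.
- Count Grade 3-4 ALT from Day 0 to 30 days after that dose in both Parts. At the least, let a later Grade 3-4 ALT count when judged IMP-related.
- Replace the clause on not counting ALT additionally with a statement that each subject is counted once.

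Use the same window for the hepatotoxicity tables in SAP 10.3, which are now limited to the treatment period, and carry it into the separate Part 2 SAP.

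The wording needs no new data. The cost is somewhat more referrals for a tolerable drug: at a true 5% rate, at most a rise from about 20% (14% if only second-week doses matter) to about 25%, if every late rise were found. In Part 1 that means DSMB review, but in Part 2 a crossing halts the regimen.

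In Arm B the wording captures only unscheduled or follow-up tests. One late liver sample, for example at Day 20-23 in all arms where a 14-day regimen runs, would close the rest for one 5 mL tube and one visit per subject. That is optional, for the sponsor to weigh. For 7-day regimens the existing Day 13 sample is enough once the window is widened.

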3.5.2.3 Dose-adjusted Arms in the Event of Toxicity

If > 10% of subjects in an arm of Part 1 meet any of the toxicity criteria, the actions shown in Table 1 may be implemented. Decisions for dose reduction will be taken based on all available safety data including the events that trigger the dose adjustment process.

Table 1. Dose Adjustment Recommendations for Toxicity Management in Part 1		
Toxicity criteria	Recommended action	Rationale
reached in		

Toxicity criteria	Recommended action	Rationale
reached in		
Arm A or Week 1 of Arm B	Halt all study arms, then begin to enrol new Arm F, Arm G, Arm H and/or Arm I with a reduced dose of ABBV-4083 300 mg QD (n=30/arm), continue to enrol the remainder of Arm E in Arm J (to a total n=30).	Presumes that dose of ABBV-4083 is too high and that albendazole does not add to the observed toxicity.
Week 2 of Arm B	Halt Arm B, then begin to enrol new Arm G with ABBV-4083 300 mg QD (n=30)	Presumes that dosing ABBV-4083 400 mg QD is safe for 7 days but not 14 days.
Arm C	Halt Arm C, then begin to enrol new Arm H with ABBV-4083 300 mg QD (n=30)	Presumes that dosing ABBV-4083 + albendazole 400/400 mg QD is safe for 3 days but not 7 days.
Arm D	Halt Arms C and D, then begin to enrol new Arms H and I with ABBV-4083 300 mg (n=30/arm)	Presumes that dosing ABBV-4083 + albendazole 400/400 mg QD is not safe.

3.5.3 Risks Associated with Disease Progression

The clinical symptoms of onchocerciasis result from inflammatory responses to the presence of mf, ranging from itching of the skin to visual impairment and blindness due to mf in the eyes. Chronic skin and ocular symptoms develop over many years. Ocular disease in onchocerciasis is characterised by changes in both the anterior and posterior segments of the eye. Early stages typically begin with the appearance of anterior punctate lesions consisting of opacities of the superficial corneal stroma. Long-standing and high-intensity infections, as measured by high levels of skin and ocular mf, can result in massive invasion of the cornea and other anterior regions, leading to later-stage disease including sclerosing keratitis, a progressive irreversible scarring of the cornea. ^{71,72} Sclerosing keratitis usually follows several years of high-intensity infection, and blindness due to this and accompanying conditions in the anterior segment, e.g. anterior uveitis, iris atrophy, anterior and posterior synechiae, secondary cataract and glaucoma, usually develop after the second decade. ⁷²

Subjects with mf in the posterior segment with certain ophthalmological history or conditions predisposing them to greater risk of ocular pathology progression, will be excluded from the study, as well as those with current hyperreactive onchodermatitis. Moreover, subjects with severe manifestations of onchocerciasis will be excluded from the study.

In order to avoid progression of ocular disease during the study, ivermectin may be used as rescue medication at any time at the discretion of the Investigator. Ophthalmological examinations will be performed at the visits at Month 3, 6, 12, 18 and 24, providing frequent opportunities to detect any ocular disease and introduce rescue medication (see Section 2.4.3). In addition, any subject with increasing microfiladermia at Month 18 compared to Month 12 will be administered ivermectin.

To minimize the risk of progression of onchocerciasis, ivermectin will be administered:

- at any time, at the Investigator's discretion if clinical symptoms and/or signs worsen. The most important goal of therapy is the continuous reduction of disease burden, i.e. mf levels (rescue medication).
- to all subjects when they reach the end of Part 1 at Month 6 (post-study IVM).
- to subjects in Part 2 with increased skin microfilariae at Month 18 compared to the number at Month 12 (rescue medication). In addition, at the 24-Month follow-up visit, ivermectin will be administered to subjects positive for microfilariae in the skin and/or eye after nodulectomy (post-study IVM).

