- Arm K (n = 84): initial treatment with an active regimen selected from Part 1, followed by ivermectin at Month 6;
- Arm L (n = 84): initial treatment with the same active regimen selected from Part 1 as Arm K, followed by ivermectin matching placebo at Month 6;
- Arm M (n = 84): initial treatment with a second active regimen selected from Part 1, followed by either ivermectin or ivermectin matching placebo at Month 6 (decision to be made prior to Part 2);

• Arm N2 (n = 84): 7 days of ABBV-4083 400 mg plus appropriate duration of albendazole matching placebo and ABBV-4083 matching placebo followed by either ivermectin or ivermectin matching placebo at Month 6 (decision to be made prior to Part 2).

In the Alternate Scenario, a minimum of 84 subjects with two or more operable sites will be enrolled to allow for approximately 21 subjects per arm to undergo a single-site nodulectomy at Month 6 for the evaluation of *Wolbachia* depletion but still have remaining onchocercomata for evaluation of skin microfilariae and other endpoints at Month 24. The overall design for Part 2 Alternative Scenario is presented in Figure 3.

Post-Study IVM rescue **IVM** Rescue Arm K Arm B. C or D IVM N = 84Arm L Same as Arm K IVM-Pbo N = 84Arm M Arm B. C or D IVM or IVM-Pbo N=84 4083-Pbo x 7d Arm N2 IVM or IVM-Pbo N=84 Alb-Pbo x 7d D6 D13 Screen D0 **M3** M6 M12 M18 M24 Skin snip Skin snip Skin snip Skin snip Skin snip Nodulectomy Nodulectomy (subset) Skin snip (1° endpoint) (Combination rule endpoint)

Figure 3. Overall Design for Part 2 - Alternative Scenario

4083 = ABBV-4083; Alb = albendazole; d = days; D = (study) day; IVM = ivermectin; M = month; Pbo = placebo

Rescue treatment with ivermectin will be offered at the investigator discretion to subjects with clinically significant worsening of symptoms and / or signs related to onchocerciasis at any time during the study or to subjects with increased mean number of microfilariae in the skin at Month 18, compared to the mean number at Month 12.

Post-study ivermectin will be provided after nodulectomy at 24 months to any subject with positive skin and/or eye microfilariae.

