8.3 Ivermectin: Rescue Medication, Post-Study, Screening Failures

Ivermectin used as described in this section for rescue medication or post-study will be provided as a single oral administration at the approved dose of 150 μ g/kg bw and is not an IMP, i.e. will not be presented as over-encapsulated tablets.

When ivermectin is administered at a follow-up or early termination visit, it must be administered only after completion of the procedures scheduled at that visit, and after confirmation of last menstrual period and a negative pregnancy test. Ivermectin will be administered to subjects under fasting conditions.

Subjects who fail screening in the communities or at the investigational centre will be referred to the National Program PNLMTN-CTP for MDA with ivermectin.

8.3.1 Rescue Medication in Part 1

In Part 1, ivermectin will be administered as rescue medication at any time during the study, at the investigator's discretion, to subjects with clinically significant worsening of symptoms and/or signs related to onchocerciasis.

8.3.2 Rescue Medication in Part 2

In Part 2, ivermectin will be proposed as rescue medication to all subjects with clinically significant worsening of symptoms and/or signs related to onchocerciasis at any time during the study and/or to subjects with increased mean number of skin microfilariae at Month 18, compared to the mean number at Month 12.

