- 13. Ophthalmological examinations: full ophthalmological examination includes ocular symptoms, ocular examinations including ocular alignment, mobility and pupillary response, visual function (visual acuity, visual field, colour vision), retinal examination and fundus photography, slit lamp examination of anterior and posterior segments and intraocular pressure. Eye microfilarial count and data for clinical outcomes in the eye will be recorded during the ophthalmological examination.
- 14. Assessments for clinical outcomes (see Study Operations Manual for details) in the skin to be performed during physical examinations where the time-points coincide.
- 15. 12-lead ECGs will be recorded in triplicate with 1 minute between recordings at all time-points. ECGs will be performed 1-2 h after intake of the IMP. ECG at early termination is only applicable if early termination is before Month 3.
- 16. Blood and urine samples for clinical laboratory safety tests (haematology, biochemistry & urinalysis (plus urine microscopy where indicated if urinalysis is abnormal and clinically significant).
- 17. IMPs will be administered daily on site and IMPs dispensation will be done via the IRT system. Treatment duration and IMPs dispensation scheme will be confirmed before start of the Part 2, depending on the regimen selected.
- 18. Administration of ivermectin must be only after completion of the procedures scheduled at the visit (including nodulectomy where scheduled), and after a negative pregnancy test. Rescue medication (ivermectin) will be offered at the investigator discretion to administer if worsening symptoms and/or signs related to onchocerciasis at any time throughout the study and/or to patients with increased mean microfilaria in the skin at Month 18, compared to the Month 12 mean value.
- 19. AE collection from signature of Informed Consent onwards. AE monitoring will be performed as specified in Section 9.3.4 and will include scheduled questioning at the indicated time-points.
- 20. In the event of certain AEs considered to be associated with the IMP, additional examinations may be conducted in order to better interpret the AE, including safety laboratory, PK, ophthalmological, physical, neurological and parasitological (eye and skin) examinations.

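### For a Month 12 to Month 18 rise in skin microfilariae in Part 2, Protocol Section 3.5.3 requires ivermectin, while Section 3.3 leaves it to the investigator's discretion

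*Protocol*

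**What the plan says.** The Month 18 rescue rule for Part 2 appears in four parts of the current protocol.

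- **Section 3.5.3 (risks of disease progression).** The running text says that "any subject with increasing microfiladermia at Month 18 compared to Month 12 will be administered ivermectin". The list that follows, headed by a statement that ivermectin will be administered, separates the triggers. One item leaves the dose to the investigator's "discretion if clinical symptoms and/or signs worsen". Another gives it "to subjects in Part 2 with increased skin microfilariae at Month 18 compared to the number at Month 12 (rescue medication", with no mention of discretion.
- **Section 3.3 (Part 2 design).** One sentence covers both triggers: "Rescue treatment with ivermectin will be offered at the investigator discretion to subjects with clinically significant worsening of symptoms" and, further on, "or to subjects with increased mean number of microfilariae in the skin at Month 18, compared to the mean number at Month 12".
- **Appendix 2, Table 8, footnote 18.** "Rescue medication (ivermectin) will be offered at the investigator discretion to administer if worsening symptoms and/or signs", continuing "to patients with increased mean microfilaria in the skin at Month 18, compared to the Month 12 mean value".
- **Section 8.3.2 (rescue in Part 2).** "In Part 2, ivermectin will be proposed as rescue medication to all subjects with clinically significant worsening" of symptoms or signs, and also to subjects with the Month 18 rise. Discretion is not mentioned for either trigger, although Section 8.3.1 does mention it for Part 1.

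Two other sections attach analysis consequences. Section 10.4 counts ivermectin rescue before Month 24 as a failure on the primary and key secondary endpoints of Part 2, in both the PP and ITT analyses. Section 10.2 keeps a rescued subject in the PP for microfilaria population even without Month 24 snips. The SAP covers Part 1 only (SAP Section 1.0), so it does not settle the point.

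**The concern.** Section 3.5.3 lists this dose among the measures that limit progression of onchocerciasis in the trial. A reader of that section will take it as assured for anyone whose skin count is rising at Month 18. An investigator working from the design section, and probably one working from the Schedule of Events, will take it as a matter of judgement. The protocol therefore does not settle whether the dose may be withheld.

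The same decision feeds into scoring. Two subjects with the same rise at Month 18 can be classified differently at Month 24 because one investigator treated and the other did not.

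**Working it through.** No figure in the plan depends on this wording, so the check is a comparison of texts followed by a count of cases.

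**Step 1. The texts side by side**

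| Protocol location | Month 12 to 18 rise | Worsening symptoms or signs |
|---|---|---|
| Section 3.5.3 | Administered; no discretion stated | Investigator's discretion |
| Section 3.3 | Offered at discretion | Offered at discretion |
| Table 8 footnote 18 | Loose syntax; most naturally offered at discretion | Offered at discretion |
| Section 8.3.2 | Proposed; discretion not mentioned | Proposed to all such subjects; discretion not mentioned |

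Only Section 3.3 is clearly contrary to Section 3.5.3. In footnote 18 the main verb governs both triggers on the natural reading, but the sentence is poorly built. Section 8.3.2 is compatible with Section 3.5.3, since a proposed dose can be given to everyone who accepts it.

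**Step 2. Can one practice satisfy all four?** Yes. A site that gives ivermectin to every subject with a rise who consents and has a negative pregnancy test (required by Section 8.3) complies with each text, because discretion includes the choice to treat. The texts part only when an investigator decides not to treat.

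**Step 3. What that decision changes.** A Month 18 mean above the Month 12 mean must exceed zero, so every triggered subject is microfilaria-positive at Month 18. Under Sections 5.1, 10.2 and 10.4:

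| Triggered subject | Rescued | Not rescued |
|---|---|---|
| Primary: Month 24 snips positive if left unaided | Failure | Failure |
| Primary: all Month 24 snips clear if left unaided | Failure | Success |
| Primary: no Month 24 snips | In PP as a failure; ITT failure | Out of PP; missing-data rule of Section 10.4 in ITT |
| Key secondary: Month 24 nodule data available | Failure | Observed nodule data |

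Among subjects with Month 24 snips, primary status therefore differs in the second row only. PP for microfilaria membership differs in the third row only. The key secondary endpoints are worm percentages per subject and do not depend on skin status, so their scoring differs for any triggered subject with nodule data.

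**Step 4. Size.** It would need the share of subjects with a rise, the share of those left untreated under discretion, and the share of those clear at Month 24 unaided. The documents give none of the three.

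**The case against.** The strongest reply is that this is an editorial matter. A site that treats every eligible subject breaks no instruction. Section 8.3.2, the section devoted to rescue, carries no discretion wording for Part 2. Footnote 18 can be read as attaching discretion to the symptom trigger alone. The list in Section 3.5.3 is also weaker evidence of a mandate than it looks, because its lead-in about administering ivermectin covers the discretionary item as well. Part 2 has yet to be finalised and will have its own SAP.

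Much of this stands. A reader might infer that a site cannot follow both sections; Step 2 shows that it can. A reader might also count Section 8.3.2 as a third conflicting rule, but its text does not contradict Section 3.5.3.

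Two things remain. The sentence quoted first from Section 3.5.3 is mandatory on its own, whatever the list adds. Section 3.3 places the same trigger under discretion without ambiguity. An offer can be squared with a required dose as respect for consent, but investigator discretion cannot, because it allows the investigator to decline to give the dose.

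**Conclusion.** The inconsistency is real, lies in current text, and should be removed before Part 2. It goes beyond wording because it decides whether a safety dose may be withheld and, through Sections 10.4 and 10.2, how a triggered subject is scored.

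Its effect on the primary endpoint is narrow and may be close to nil, since most routes through Step 3 end in failure either way. Key secondary scoring is more exposed, but its size is equally unknown.

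Two stronger readings are not supported:

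- **That the Part 2 power is misstated.** Section 10.3.2 does not say whether its planned clear rates already count rescue as failure, and nothing in the documents shows a stated power to be wrong.
- **That discretion favours one arm.** Treatment is double-blind (Section 7.4.1), so the decision is made without knowledge of the assigned arm.

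The conclusion assumes only that the quoted sentences carry their ordinary meaning. It needs no assumed event rate.

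**What to change.** Before Part 2 starts:

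1. Amend Section 3.3 and Table 8 footnote 18 so that discretion applies only to worsening symptoms or signs. State separately that when the Month 18 mean exceeds the Month 12 mean, ivermectin is administered, subject to the subject's consent and a negative pregnancy test.
2. Use the same Month 18 wording in Section 8.3.2. Do not add discretion for the symptom trigger there as a side effect. That section now proposes ivermectin to all subjects with clinically significant worsening, and narrowing it should be an explicit sponsor decision.

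Optionally, report by arm how many subjects met the Month 18 trigger and how many were rescued. The scheduled skin snips and the medication records under Section 8.1 already supply both counts.

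The cost is a few sentences in three places, with no new data and no change to sample size. The pause between the two parts described in Section 3.1 gives time to make the change.
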